Train Your Brain: A Pilot Project to Improve Memory and Decision Making

NCT05879198

Final Approved Protocol

Document Date 8/16/2024

Data Analytic Plan

Primary Outcomes: Changes in delay discounting, time horizon, and executive functions.

Descriptive statistics will be used to characterize the sample and psychometric properties will be examined (reliability, etc.). Changes in quantitative measures (including delay discounting, time horizon, and executive functions) will be examined in a number of ways. First, we will examine each variable to evaluate mean, standard deviations, skew and kurtosis. We will examine the overall number of youth who demonstrated decreases in delay discounting (5-Trial Adjusting Measure of Delay Discounting). We will use *t*-tests and reliable change indices (RCI) to examine differences in mean levels of consideration of future consequences (Consideration of Future Consequences Scale) and measures of executive function (Tower of Hanoi, Letter Number Sequencing, Iowa Gambling Task). We will set statistical significance at $p < .05$.

Secondary Outcomes: Changes in risk behaviors.

Descriptive statistics will also be examined for all secondary outcomes. We will then evaluate changes in our measures of risky behaviors (the Youth Risk Behavior Survey and the Alcohol and Marijuana Expectancies measures) using *t*-tests and RCIs. We will set statistical significance at $p < .05$.

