All other assessments will be double-entered and cleaned by research staff. Data files will be backed up weekly and stored on a password-protected computer. Staff will attempt to collect all missing assessments immediately post collection but no later than 1 month after study completion. Missed or incomplete assessments are anticipated. As a result, study staff will document the reason why assessments are missed in the study files. Missed assessments will not be documented or reported as protocol deviations for the purposes of this study.

Power Analysis and Sample Size Considerations. The primary purpose of this grant is to establish implementation factors and detect signal in constructs of interest (i.e., DD and WM) in preparation for a subsequent, fully-powered trial. Therefore, we present information

regarding required sample size for completeness, but highlight that this project is not intended to be powered to examine clinical effectiveness.

Missing Data. Because missing data can lead to biased estimates of effects and, consequently, incorrect interpretations of clinical trial outcomes, we will attempt to handle missingness in a number of ways, including employing participant retention procedures and collecting assessments even if the participant did not complete any or all of the computer training sessions. If data is missing, we will examine patterns of missingness to determine if specific missing data algorithms, such as multiple imputation or full information maximum likelihood approaches, would be appropriate for use with our data.

Next Steps. Findings for the current study will provide critical information for successfully completing future aims of this grant, including an RCT examining effectiveness of WM training in reducing adolescent DD and risk for SU, guided by the results of the current study. Results may also support utilizing the intervention adjunctively alongside more content-focused prevention efforts, supporting future comprehensive prevention trials to decrease SU. Developing cognitive training interventions targeting mechanisms of SU liability specific to adolescents exposed to early adversity has the potential to enhance both basic understanding of determinants of SU and intervention approaches in a vulnerable, traditionally underserved adolescent population.

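### Four of the five primary measures are t-tested at .05 with no ranking or adjustment, while delay discounting gets only a count; neither that count nor the RCIs have a chance benchmark

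*SAP*

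**What the plan says.** The SAP's primary paragraph is headed "Primary Outcomes: Changes in delay discounting, time horizon, and executive functions" and ranks none of the three domains. Its analyses are:

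- **Delay discounting:** "We will examine the overall number of youth who demonstrated decreases in delay discounting (5-Trial Adjusting Measure of Delay Discounting"). No test, interval or expected count is given.
- **Time horizon:** t-tests together with "reliable change indices (RCI) to examine differences in mean levels of consideration of future consequences", measured by the Consideration of Future Consequences Scale.
- **Executive function:** the same two methods for "measures of executive function (Tower of Hanoi, Letter Number Sequencing, Iowa Gambling Task").
- **Threshold:** "We will set statistical significance at $p < .05". Multiplicity is not mentioned, and no RCI cut-off or source of reliability is given.

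The secondary paragraph applies t-tests and RCIs at the same threshold to "the Youth Risk Behavior Survey and the Alcohol and Marijuana Expectancies measures".

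The protocol (section 3, Power Analysis and Sample Size Considerations) describes the purpose more narrowly: to establish implementation factors and "detect signal in constructs of interest (i.e., DD and WM) in preparation for a subsequent, fully-powered trial". It adds that the project is not meant to be powered for effectiveness. Up to 50 youth enrol and all receive the active training (section 3, Procedures for Intervention Group).

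**The concern.** The protocol names two constructs in which a signal is sought, delay discounting and working memory. The SAP makes five instruments primary, and its formal testing does not match that aim. The construct that the training is meant to move has no test, while four other measures each have one at .05. Nothing says which result, or how many, would count as a signal.

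The protocol (section 3, Next Steps) says that the later randomised trial will be guided by these results, so what is called a signal here has a use. Three things would be hard to interpret:

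- one significant result out of four;
- a count of youth whose discounting fell, with no comparison figure;
- a small number of reliable improvers, with no statement of how many to expect among youth who have not changed.

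The RCI sentence also mixes two questions. A t-test concerns the mean; an RCI concerns whether one person's change exceeds measurement error.

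**Working it through.** The documents give no power calculation and no family-wise error rate, so there is no figure of theirs to reproduce beyond the per-test .05.

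**Inputs from the documents.** Four t-tested primary measures; this is a minimum, because the score taken from each task is not specified. Three secondary measures, if the alcohol and marijuana expectancies count separately. Per-test level .05. Up to 50 youth.

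**Assumptions.** Two-sided tests. RCI cut-off ±1.96. Under no change, discounting is equally likely to rise or fall.

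**1. At least one false positive among the t-tests.**
- Four independent tests, either direction: 1 − 0.95^4 = 0.185.
- Favourable direction only: 1 − 0.975^4 = 0.096.
- Correlated change scores (simulated, n=50, either direction): about 0.17 at r=0.3, 0.155 at r=0.5 and 0.13 at r=0.7. Favourable direction only: about 0.087, 0.077 and 0.065.
- Adding the three secondary measures, independent: 1 − 0.95^7 = 0.302; favourable only, 1 − 0.975^7 = 0.162.

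**2. Delay discounting count.**
- Expected number decreasing by chance: 50 × 0.5 = 25. A majority (26 or more) decreases with probability 0.44.
- If ties lower the chance of a decrease to 0.4, the expected number is 50 × 0.4 = 20.

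**3. RCI counts.**
- At ±1.96, 2.5% of unchanged youth fall beyond the cut-off in each direction: 50 × 0.025 = 1.25 per measure each way.
- A count threshold is not a safe decision rule. Four or more improvers out of 50 on one measure has chance probability 0.036. Across four independent measures, the chance that at least one reaches four is 1 − (1 − 0.0362)^4 = 0.137.

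**4. What these benchmarks leave out.** There is no control arm, and the tasks are repeated after five to seven weeks. As an illustration only, assume a pure retest gain of 0.2 SD of the change score at n=50. One t-test is then significant in the favourable direction 28% of the time, and at least one of three independent executive function tests 63% of the time (1 − 0.717^3). For assumed gains of 0.1 to 0.3 SD, the latter figure runs from 28% to 91%. No multiplicity adjustment removes this.

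**5. Cost of Holm over two measures.** Paired t-test, n=50, change of 0.4 SD (an assumed effect): power 0.79 at .05 and 0.70 at .025, the stricter Holm step.

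**The case against.** This is an unpowered pilot whose aims are feasibility, acceptability and dosage, so strict family-wise control is optional. That stands, and it is why labelling the tests exploratory is an acceptable alternative below. It does not explain why the SAP uses the word primary and a significance threshold without saying how the results are to be read.

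The contrast with the protocol should not be pressed too far. Sections 1, 2 and 5 also treat executive functions as relevant to the study, and the SAP itself ties time horizon to a named scale. The mismatch lies in which measures are primary and tested. Measuring the others is not at fault.

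The RCI sentence may be loose drafting, with t-tests meant for means and RCIs for individuals. That is the natural reading, and the SAP should state it.

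A reader might infer that a false signal is likely, since the chance of at least one false reliable improver is 72% on one measure at n=50 (1 − 0.975^50) and over 99% across four independent measures (1 − 0.975^200). The documents do not support this. Both figures need the assumed 1.96 cut-off and a rule that a single improver counts as a signal, and the SAP contains neither. On the t-tests alone the risk is about 1 in 5, or about 1 in 10 in the favourable direction.

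**Conclusion.** The point holds as a moderate weakness that is cheap to repair. With no true change, the four primary t-tests carry an 18.5% chance of at least one p<.05 if independent, about 13% to 17% at correlations of 0.7 to 0.3, and 9.6% (independent) for favourable results only. The last figure compares with 2.5% for a single two-sided test; the others compare with 5%. Delay discounting has no formal analysis, and its count means little without the 25 of 50 expected under equal chances of rise and fall. RCIs need a stated cut-off and an expected count, and should be kept to individuals.

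These sizes rest on two-sided testing, four scores in all, and no retest or maturation shift. The last is doubtful in a single-arm study with repeated cognitive tasks, where such a shift could mislead more than multiplicity does.

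**What to change.** Change the SAP wording as follows.

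1. Name one delay discounting score and one working memory score (for example Letter Number Sequencing) as primary, in line with the protocol's two signal constructs. Report the paired mean change with a 95% CI for each, and state that this adds a delay discounting analysis the SAP now lacks. Either apply Holm over the two at .05 or label both tests exploratory.
2. Report Consideration of Future Consequences, Tower of Hanoi and Iowa Gambling Task as mean change with 95% CI, without a significance claim.
3. Use t-tests or intervals for means and RCIs for individuals only. State the RCI cut-off and the source of the reliability value. For each measure, give the numbers reliably improved and reliably deteriorated beside the number expected by chance (1.25 of 50 each way at ±1.96). Report discounting decreases beside increases and ties.
4. Do not turn any of these counts into a pass mark, and state that retest gains can push results past the chance benchmarks because there is no control arm.

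The cost is that fewer results can be called significant. If Holm is used, power for a 0.4 SD change at n=50 falls from about 79% to about 70% at the stricter step. No extra data are needed.

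### Delay discounting is the only named instrument the SAP leaves out of its t-tests and reliable change indices; its one specific analysis is a count of decreases

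*SAP*

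**What the plan says.** The SAP's Primary Outcomes paragraph names changes in delay discounting, time horizon and executive functions, in that order and without a stated hierarchy. It opens with a general statement that takes in DD: "Changes in quantitative measures (including delay discounting, time horizon, and executive functions) will be examined in a number of ways". The first step is descriptive: "First, we will examine each variable to evaluate mean, standard deviations, skew and kurtosis". The DD-specific sentence follows: "We will examine the overall number of youth who demonstrated decreases in delay discounting (5-Trial Adjusting Measure of Delay Discounting".

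The next sentence assigns t-tests and RCIs to the Consideration of Future Consequences Scale and to "measures of executive function (Tower of Hanoi, Letter Number Sequencing, Iowa Gambling Task". The Secondary Outcomes paragraph assigns the same two methods to "the Youth Risk Behavior Survey and the Alcohol and Marijuana Expectancies measures". Both paragraphs set significance at p < .05. Neither says that the t-tests are paired.

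The protocol adds no DD analysis. Section 3, Power Analysis and Sample Size Considerations, gives as a main purpose to "detect signal in constructs of interest (i.e., DD and WM) in preparation for a subsequent, fully-powered trial", and adds that "this project is not intended to be powered to examine clinical effectiveness". Elsewhere in section 3, up to 50 youth are enrolled, all receive the active training, and each is assessed once before the sessions and once straight after them.

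**The concern.** DD is the construct the training is meant to change, and the protocol names it as one in which a signal is sought for a later trial. Planning that trial calls for the mean within-person change in DD, its SD and its uncertainty. The SAP assigns a mean comparison and an individual-level index to every other named instrument, secondary ones included, but gives DD only a tally of how many youth moved downward.

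A tally treats a trivial decrease and a large one alike. Because no minimum decrease is stated, random fluctuation between two measurements is enough to be counted. Youth whose score did not change are not mentioned, so a published count could leave open whether the remainder got worse or stayed the same.

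**Working it through.** The plan states no DD sample size, effect size or SD, so there is no figure of its own to reproduce. The check has three parts.

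**1. Instruments against assigned analyses (SAP)**

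| Instrument | Outcome | Descriptives | t-test and RCI | Count of decreases |
|---|---|---|---|---|
| 5-Trial Adjusting DD | Primary | Yes | No | Yes |
| Consideration of Future Consequences | Primary | Yes | Yes | No |
| Tower of Hanoi | Primary | Yes | Yes | No |
| Letter Number Sequencing | Primary | Yes | Yes | No |
| Iowa Gambling Task | Primary | Yes | Yes | No |
| Youth Risk Behavior Survey | Secondary | Yes | Yes | No |
| Alcohol and Marijuana Expectancies | Secondary | Yes | Yes | No |

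DD is the only row without a t-test and RCI.

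**2. How noisy the count is**

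Inputs: n = 50 is the protocol's ceiling. Completer numbers of 40 and 30 are assumptions; the protocol expects missed assessments but gives no rate. Suppose no true change, change scores symmetric about zero, and no ties. The count X is then Binomial(n, 0.5).

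| n | Expected decreases | 2.5th to 97.5th percentile | P(60% or more decrease) |
|---|---|---|---|
| 50 | 50 × 0.5 = 25 | 18 to 32 | P(X ≥ 30) = 0.101 |
| 40 | 20 | 14 to 26 | P(X ≥ 24) = 0.134 |
| 30 | 15 | 10 to 20 | P(X ≥ 18) = 0.181 |

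Ties change what a count means. Take 25 decreases among 50. If none are unchanged, there are 50 − 25 = 25 increases, and a two-sided sign test gives p = 1.00. If 15 are unchanged, there are 50 − 25 − 15 = 10 increases, and the same test with ties excluded gives p = 0.017. The figure of 15 is illustrative; no document gives a tie rate.

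The information lost by ignoring size can be illustrated at n = 50 with normal change scores and a two-sided 0.05 level. For a standardised mean change of 0.3, a paired t-test has power 0.55 and a sign test on the same data 0.32. At 0.5 the figures are 0.93 and 0.74. The effect sizes are assumptions, and the SAP plans no sign test.

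**3. What precision the plan assures for mean DD change**

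With change scores in hand, the 95% half-width in units of the SD of change is t(0.975, n−1)/√n:

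- n = 50: 2.010/7.071 = 0.284
- n = 40: 2.023/6.325 = 0.320
- n = 30: 2.045/5.477 = 0.373

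If the planned descriptives cover only the pre and post scores, the difference in means is still available among youth with both assessments, but the SD of change is not. With equal pre and post SDs, SD of change = SD × √(2(1 − r)), where r is the pre-post correlation. Over an assumed range at n = 50:

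- r = 0.3: √1.4 = 1.183, half-width 1.183 × 0.284 = 0.336 raw SD
- r = 0.8: √0.4 = 0.632, half-width 0.632 × 0.284 = 0.180 raw SD

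The same pre and post descriptives are thus compatible with intervals that differ almost twofold in width (0.336/0.180 = 1.87).

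**The case against.** The strongest reply is that this is a small, open-label feasibility series, expressly not powered for effectiveness, and that a descriptive responder count is a reasonable summary in one. DD is also not bare of mean-level information. The descriptives cover it, and the general sentence on changes names it. Both points stand. A reader might infer that DD change will not be estimated at all, or that a powered test has been left out; the documents support neither. What remains is that pilot status does not explain the omission, since the same SAP plans t-tests and RCIs for everything else. If the general sentence was meant to bring DD under the t-tests, the sentence that lists the instruments does not say so.

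A reader might also infer that the other measures are promised an interval and an SD of change that DD is denied. They are not: the SAP promises neither for any instrument, and it gives no reliability value for any RCI. Only the missing t-test and RCI are specific to DD.

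Finally, one might fault the SAP for giving no reference proportion for the count. That is weak. A 50% benchmark presumes symmetric change in the absence of an effect, which practice or regression to the mean would break, and no document supports another benchmark. The binomial figures show how much noise a bare count carries; they do not supply a benchmark to test against.

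**Conclusion.** The point holds as a gap in estimation that is cheap to close. The omission is plain from the SAP's text. Its consequence is narrower: the point estimate of mean DD change would probably be recoverable from the descriptives, but its precision is assured only if those descriptives include change scores, which the SAP does not say.

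The size: with no change and no ties, a count out of 50 ranges from 18 to 32, and reaches 30 or more one time in ten. A paired estimate on the same 50 youth would give the mean change to within 0.28 SD of change. The tie, correlation, effect-size and reduced-completer scenarios are assumptions and serve only as illustration.

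It would go too far to conclude that a paired analysis would show whether training works. With one arm, neither the count nor the mean change separates training from practice or regression to the mean.

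**What to change.** In the SAP's Primary Outcomes paragraph:

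- Add DD to the sentence that assigns t-tests and RCIs, and state that the test is paired.
- Fix the scale on which DD is analysed before data are seen, for example the log of the discount rate.
- Report mean within-person change in DD with the SD of change and a 95% CI.
- Keep the count, reported as decreased, unchanged and increased.
- State that the result describes change over the training period and does not attribute it to training.

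The cost is SAP wording, one more analysis, and a scale that must be chosen in advance. No new data are needed, because the planned count already requires DD at both assessments. An RCI for DD needs a reliability value, as it does for every other instrument. The SAP says that "psychometric properties will be examined (reliability, etc" but does not say which value the RCIs will use; that is a general matter for the SAP and not part of the DD gap.
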